# 1. Background and Significance

Among 4 million infants born annually in the US, nearly 0.5 million are born prematurely (<37 weeks gestation) and cared for in Neonatal Intensive Care Units (NICUs). These preterm infants are extremely vulnerable in the perinatal period, with increased risks of physiologic instability, apnea, chronic intermittent hypoxemia, impaired temperature and metabolic regulation, and infection (1-7). Such prematurity-related complications are the leading cause of neonatal mortality and morbidity and result in longer average lengths of hospital stay and higher rates of re-hospitalization in preterm infants than in full term infants. Strategies to improve the physiologic stability and maturation of preterm infants during the critical perinatal period are vital to improve preterm infant outcomes, reduce life-long morbidity, and mitigate associated healthcare costs.

Skin-to-skin contact between a preterm infant and a parent, also known as kangaroo care (KC), is an important, inexpensive modality deployed in the NICU to support the infant's development and the formation of the parent-infant bond. During KC, a parent holds an infant against their bare chest, skin-to-skin. NICU implementation of KC typically involves the mother (8), in a practice familiarly termed Kangaroo Mother Care (KMC). Over 1,000 articles supporting the implementation and positive effects of KMC have been published, outlining the positive effects of KMC intervention on physiologic and psychosocial outcomes. KMC is invaluable in promoting strong mother-infant bonds, reducing morbidity and mortality, improving infant physiologic stability, and benefiting overall development trajectories. Additionally, KMC has also been shown to greatly benefit mothers, with improved initiation and duration of breastfeeding, reduced anxiety, and improved sense of confidence in parenting (10).

In contrast to KMC, conspicuously little research has been published about the implementation and benefits of Kangaroo Father Care (KFC). The limited preliminary data that are available support an association between KFC and improved preterm infant physiologic stability (e.g. heart rate variability, respiratory status, blood glucose, oxygen saturation (13)), infant contentment (e.g. crying episodes (12), time to relaxed state (13) and father-infant bonding (12). While both mothers and fathers have been noted to experience doubt, stress, anxiety, depression and loss of control (16) in the NICU, fathers are faced with different challenges than mothers (17,18). Specifically, fathers have been shown to feel less important and less needed than mothers (19), un-empowered in terms of active participation at the bedside, and relegated to return to work and handle external affairs (20). Fathers also report a lack of confidence in how to interact with and care for their premature infant, including a fear of caring for the infant based on the infant's size and perceived fragility (17). Research suggests that these feelings can interrupt the father-infant bond (21). Additionally, fathers have been shown to hide their feelings and return to work while their infant is still in the NICU (19, 22-24) and to experience "pervasive uncertainty" when transitioning home (18). These feelings and experiences may further translate into individual and interpersonal stress, anxiety, and diminished parenting confidence. KFC may be an effective mechanism to support fathers through these experiences, so they can, in turn, better support infants and mothers.

Even though the short and long-term benefits, including cost-effectiveness, of KMC are clear and the World Health Organization recommends that KC be utilized as continuously as possible during the neonatal period (9), the benefits of KFC are only emerging and KC remains thoroughly under-utilized (14) in the NICU (15). We propose to revolutionize KC in the NICU by objectively measuring the effects of the KFC intervention on infants, fathers, and families. Utilizing wireless biosensor technology designed

by members of this team, our study will be the first of its kind to objectively evaluate KFC as an intervention for improving both acute and long-term outcomes of infants, mothers, and fathers in the NICU.

# 2. Study Hypothesis and Outcomes

# 2.1. Study Hypothesis

The main hypothesis of this study is that Kangaroo Father Care (KFC) will positively impact acute physiologic and long-term behavioral outcomes in infants, fathers, and families.

# 2.2. Outcome Measures

## 2.2.1. Primary Outcome

Primary outcome measures include heart rate (HR) and oxygen saturation (SpO2) as indicators of cardiorespiratory stability in infants before, during, and after KC and HR and HR variability (HRV) as indicators of physiologic stress in NICU parents during and after periods of KC. All of these outcomes will be measured using wearable, wireless biosensors.

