## 2.2.2. Secondary Outcomes

Secondary outcome measures include 1) Accelerometry data captured using the wearable biosensors and compared to observations of infant position made by a study team member during KC sessions to validate the accuracy of these biosensors in detecting body position and movement during KC; 2) Infant salivary cortisol reactivity, maternal salivary cortisol reactivity, and paternal salivary cortisol, testosterone, and oxytocin reactivity, compared before, during, and after KC; 3) Parenting confidence, relationship quality, and involvement scores as quantitated by the Parenting Sense of Competence Scale (PSOC), the Revised Dyadic Adjustment Scale (RDAS), the Postpartum Bonding Questionnaire, and a Father Involvement Scale at baseline, before discharge, two weeks after discharge, and four weeks after discharge. Two-sample t tests and mixed-effect linear regression models will be used to assess the mean between-group differences. Covariates such as age, education, socio-economic status (SES), stress and depression will be adjusted in the multivariable regression model.

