#### **Physiologic Recording:**

*Infant*: Prior to the first scheduled KC session, two wearable, wireless biosensors will be placed on the infant to continuously capture physiology measures including electrocardiogram (ECG), heart rate (HR), oxygen saturation (SpO2), body temperature, respiratory rate, movement, systolic blood pressure (BP-S), and others for the duration of the study. One device will be placed on the infant's chest or back. A second device will be placed peripherally, on the infant's leg, foot, arm, or hand. The devices are encapsulated in a medical-grade silicone and will be adhered to the infant's skin using a medical-grade adhesive, similar to the adhesives standardly used in the NICU. The biosensors will be left in place for up to 48 hours, but will be checked by study staff at least once every 24 hours to ensure skin integrity and signal quality. The adhesives will be changed between uses.

**Parent:** The same type of wearable, wireless biosensor will also be used to record 4 hours of continuous physiology including ECG, HR, temperature, movement, SpO2, and others in the infant's parents. The biosensor will be placed on the parent's chest 1 hour before the start of a scheduled KC session and worn for 1 hour preceding the scheduled KC session, during the 2-hour KC session, and for 1 hour after the completion of the KC session. The biosensor will be worn by the parents for approximately 4 hours in total.

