# 5. Statistical Analysis

## 5.1. Statistical Plan

Measurements made through clinical standard of care will be compared to the measurements recorded by the wearable sensors. Distribution checks for normality and data accuracy will be completed for each individual and for the entire study prior to all analyses. For continuous measures of physiology, 30 second epochs will be defined for each method for comparison.

Agreement and correlation of wearable biosensor measures to standard of care measures will be assessed in two ways. First, Bland–Altman plots will be created to assess agreement between each measurement system via bias and precision, which reflect the mean or average difference between two methods and the variation in these differences, respectively. Our second method consists of individual correlations between methods assessed for each person. This correlational method will supplement additional methods, and can be directly transformed to variance shared between wearable biosensor and standard of care measures, a common metric of reliability of any measure.

Formal tests of bias, precision, and correlations: While the above methods will yield useful statistics, they need to be extended to deal with the structured nature of our data. Specifically, our data are clustered, meaning that we have multiple observations within each person and multiple people in our sample, which violates standard independence assumptions inherent to many models. We propose to estimate bias and correlation/reliability using multi-level models, which yield the same statistics discussed above but account for the fact that observations taken from the same patient are more related than comparisons involving different patients.

Data will be cleaned and analyzed using IBM SPSS Statistics 20.0, unless a newer version of SPSS is available. Using repeated-measures analysis of variance (RM-ANOVA), with the study phase (pre-, during-, and post-kangaroo care) as the repeated factor, we will test differences across study phase for maternal cortisol, paternal cortisol, infant cortisol, paternal oxytocin, and paternal testosterone. We will use a two-tailed test with a 5% level of significance analysis. In addition to tracking changes over the period of kangaroo care, we will also examine within-triad correlations in cortisol for mother-father-

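### The parental primary outcome (HR, HRV) omits the recorded pre-session hour; separately, the only pre/during/post analysis covers none of the primary physiologic outcomes

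*Combined protocol and SAP*

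**What the plan says.** **Outcome windows.** One sentence in Section 2.2.1 sets two different windows. Infant HR and SpO2 serve "as indicators of cardiorespiratory stability in infants before, during, and after KC". The parental part reads "HR and HR variability (HRV) as indicators of physiologic stress in NICU parents during and after periods of KC". Section 2.2.2 uses all three phases for the saliva outcomes, including "paternal salivary cortisol, testosterone, and oxytocin reactivity, compared before, during, and after KC".

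**Recording.** Section 3.3 (Physiologic Recording, Parent) says: "The biosensor will be placed on the parent's chest 1 hour before the start of a scheduled KC session". The sensor is then "worn for 1 hour preceding the scheduled KC session, during the 2-hour KC session, and for 1 hour after" the session ends. The pre-session hour is therefore a planned part of the parental recording.

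**Analysis.** Section 5.1 has one model with a phase factor, a repeated-measures ANOVA "with the study phase (pre-, during-, and post-kangaroo care) as the repeated factor". Its dependent variables are listed: "we will test differences across study phase for maternal cortisol, paternal cortisol, infant cortisol, paternal oxytocin, and paternal testosterone". The other analyses that Section 5.1 gives for sensor signals compare the wearable with standard-of-care monitoring. They address device agreement, not an effect of KC. The t tests and mixed models in Section 2.2.2 stand under the secondary outcomes and do not name HR or HRV.

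**Hypothesis.** Section 2.1 states that "Kangaroo Father Care (KFC) will positively impact acute physiologic and long-term behavioral outcomes in infants, fathers, and families".

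**The concern.** The hypothesis is about an impact on acute physiology, in fathers among others. An impact has to be measured from some reference level. According to Section 3.3, each family has one maternal and one paternal KC session, and each parent is recorded for about 4 hours in total. No parental recording away from KC is described. The hour before the session is thus the only pre-KC HR/HRV reference that the documents describe for a parent, and the outcome definition leaves it out.

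With only the during and after phases, the available within-parent contrast is during versus after. A parent who did not respond and a parent whose response lasts through the following hour look the same on that contrast. The plan measures the post-session hour as an outcome phase in its own right, so persistence cannot simply be assumed to be zero.

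A comparison of fathers with mothers would not supply the missing reference. Session order is randomised and parent role is not, so any resting difference between mothers and fathers would stay in the comparison.

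**Working it through.** The plan states no figure on this point, so there is none to reproduce. The check sets the sections side by side and then asks what each contrast can show.

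**1. Where each phase is used**

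| Measure | Phases in outcome definition | Phases collected | In the Section 5.1 phase analysis? |
|---|---|---|---|
| Infant HR, SpO2 | before, during, after (2.2.1) | continuous (3.3) | no |
| Parental HR, HRV | during, after (2.2.1) | 1 h before, 2 h during, 1 h after (3.3) | no |
| Salivary markers | before, during, after (2.2.2) | T1, T2, T3 (3.3) | yes, five markers |

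Two facts follow. Parental HR/HRV is the only row whose definition is narrower than its data collection. The absence from the phase analysis affects both physiologic rows, including the infant row, whose definition does contain the pre-KC phase. These are two separate gaps.

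**2. Recording time.** 1 h + 2 h + 1 h = 4 h, which agrees with the total in Section 3.3. The defined outcome covers 2 + 1 = 3 of those 4 hours.

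**3. What the contrasts estimate.** Let m be a parent's pre-session level, d the effect during KC and a the effect still present afterwards. If nothing else differs between phases:

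- pre = m
- during = m + d
- after = m + a
- during − after = d − a
- during − pre = d
- after − pre = a

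During and after alone give two means for three unknowns, so only the difference d − a can be estimated. If a share f of the effect persists, a = f·d and during − after = (1 − f)·d.

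**4. Illustration with assumed heart rates (not from the documents)**

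| Case | Pre | During | After | During − after | During − pre | After − pre |
|---|---|---|---|---|---|---|
| Effect persists fully | 80 | 75 | 75 | 0 | −5 | −5 |
| No effect | 75 | 75 | 75 | 0 | 0 | 0 |

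For an assumed d = −5, during − after is:

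- f = 0: (1 − 0) × (−5) = −5
- f = 0.5: (1 − 0.5) × (−5) = −2.5
- f = 1: (1 − 1) × (−5) = 0

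During − pre is −5 in all three cases. The documents give no value for f, so its whole range from 0 to 1 is open. At f = 0 nothing is lost.

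**5. Limit of the pre-session reference.** Adding the pre hour gives three means for three unknowns only if that hour represents the resting level and nothing but KC changes between phases. Section 3.3 sets no rest, posture or activity standard for the hour. If posture, activity or time adds an amount p during KC, then during − pre = d + p, and the phase means alone cannot separate d from p.

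**The case against.** **The real gap is the missing analysis.** This is largely right. Infant HR/SpO2 is defined with a pre-KC phase and still has no effect analysis in Section 5.1. A reader might infer that the parental wording is the cause of the missing analysis; the infant case shows that it is not. Changing Section 2.2.1 alone would change no planned analysis. The wording still matters because it is the definition of a primary outcome. A phase model fitted strictly to it would have two parental phases, and no other section assigns the pre-session hour to HR/HRV.

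**It is probably a dropped word.** That is plausible, given the scheduled pre-session hour and the three phases used elsewhere. Defining an outcome window also does not forbid using an earlier recording as a baseline. But no text says that this is intended, and the sentence gives infants and parents different windows.

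**The loss is not measured.** This stands. A reader might take the one hour in four outside the definition as a 25% loss of information, or the (1 − f) series as the expected attenuation. Neither reading is supported. The first is a share of recording time, and the second rests on assumed values and on a contrast that the plan never names.

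**The pre hour is not a clean baseline.** This also stands, for the reason in step 5 of the working. It calls for a stated caution and a check, not for discarding the hour.

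**Change scores are a preference.** A reader might infer that a mother-father comparison must use change scores. The plan specifies no such HR/HRV comparison, and change scores remove a resting difference in full only if it is constant. Other ways of using the pre-session hour are defensible.

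**Conclusion.** The point holds in two parts. First, the parental HR/HRV outcome in Section 2.2.1 omits a pre-session period that Section 3.3 records. Second, and independently, no pre/during/post analysis is written for any primary physiologic outcome, parental or infant. Both rest on the text alone and need no assumed number.

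The consequence is qualitative. If the stated window is followed, the parents' only described pre-KC reference is unused, and what remains cannot distinguish no response from a persisting one. The size of that loss depends on how much of any effect carries into the post-session hour. The documents do not say, and the loss could be nil. The claim that the pre hour would fully identify the effect is also too strong, because it assumes no posture, activity or time effect.

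This should be changed because it concerns a primary outcome and the data are already collected. It does not show that the trial fails.

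**What to change.** 1. **Section 2.2.1:** add the pre-session period to the parental HR/HRV outcome, so that its three phases match those for infants.
2. **Section 5.1:** add parental HR and HRV, and infant HR and SpO2, to the pre/during/post repeated-measures or mixed-model analysis, with phase as a within-person factor. Report during minus pre and post minus pre.
3. **Interpretation:** state that during minus pre may also reflect posture, activity or time, and check this with the movement signal that the sensor already records.
4. **Any mother-father comparison:** use the pre-session hour as the reference, through a phase-by-parent term, a change score or baseline adjustment. The choice is for the trial statistician.

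**Cost:** no new data, visits or devices. The outcome edit is a single word. The analysis edit needs a little more thought: Section 2.2.1 names no HRV measure, and the 30-second epochs in Section 5.1 are defined for comparing measurement methods. The HRV measure and the summary of each phase therefore have to be written down as well.

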#### Standard of Care Data Collection:

In all patients in rooms where data from standard of care monitoring is recorded on the BedMaster system, this data will be used for comparison to data captured using the wearable sensors. In participants in rooms where this system is not available, the MediCollector system will be used to capture background data during the approximately 48-hour study.

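### Infant HR and SpO2 are measured only with the wearable sensor, but the agreement analysis has no KC-phase term, so an error specific to KC would be diluted there and enter the primary phase contrast in full

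*Combined protocol and SAP*

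**What the plan says.** Section 2.2.1 sets the infant primary outcomes as "heart rate (HR) and oxygen saturation (SpO2) as indicators of cardiorespiratory stability in infants before, during, and after KC", and adds for all primary outcomes: "All of these outcomes will be measured using wearable, wireless biosensors". No second source is named.

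Section 5.1 makes the sensor's performance a study question: "Measurements made through clinical standard of care will be compared to the measurements recorded by the wearable sensors", and "Agreement and correlation of wearable biosensor measures to standard of care measures will be assessed in two ways". The methods are Bland-Altman bias and precision, a correlation for each person, and multilevel models that allow for repeated observations on the same person. Epochs of 30 seconds are used. No KC phase, no session and no analysis window is mentioned for these models. Study phase appears in 5.1 only as the repeated factor for the salivary hormones.

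The one validation tied to KC is in section 2.2.2. It concerns accelerometry, and its aim is "to validate the accuracy of these biosensors in detecting body position and movement during KC".

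Reference data are already being recorded. Under Standard of Care Data Collection in section 3.3, for rooms with BedMaster, "this data will be used for comparison to data captured using the wearable sensors"; in other rooms, "the MediCollector system will be used to capture background data during the approximately 48-hour study". No repeat of the infant primary contrast on these data is planned.

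**The concern.** The infant primary question is a change across phases. A sensor error that is constant over the record cancels in such a contrast; an error that appears only during KC does not. The agreement analysis should therefore estimate how sensor error differs between phases, and as written it has no term that does so.

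The possibility is not far-fetched. Physiologic Recording in section 3.3 puts one of the two infant devices on the chest or back, and KC places the infant against the parent's bare chest. Section 2.2.2 already treats accuracy during KC as worth checking for position and movement, but nothing similar is set out for HR and SpO2.

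At stake is the reading of the before/during/after result. A shift that comes from the sensor could be reported as a change in cardiorespiratory stability, next to an overall agreement figure that looks acceptable.

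**Working it through.** **The plan's own figure.** The documents give no agreement target or expected bias to reproduce. The only design figure is power above 99% in section 5.1. It cannot be reproduced because no sample size, effect size, SD or intraclass correlation is given, and this point does not depend on it.

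**Inputs from the documents**
- KC time: two sessions of 2 h = 4 h (section 3.3, Kangaroo Care Intervention).
- Infant sensor wear: "The biosensors will be left in place for up to 48 hours" (section 3.3, Physiologic Recording).
- Epoch: 30 s, so 120 per hour (section 5.1).

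**Assumed inputs**
- Sensor-minus-monitor bias is a outside KC and a + b during KC, with b = 2, 3 or 5 units (SpO2 points or bpm).
- SD of the differences within a phase: s = 2 units.
- Window analysed: 48 h, 24 h, or 8 h (1 h before, 2 h KC and 1 h after, twice).

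**Formulas.** Let p be the KC share of the epochs.
- Error in the during-minus-before contrast: (a + b) − a = b.
- Overall bias: a + p·b. The part due to KC is p·b.
- Overall SD of differences: √(s² + p(1 − p)b²). The half-width of the limits of agreement is 1.96 times this.

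**KC share at 48 h:** (4 × 120)/(48 × 120) = 480/5,760 = 0.083, or one-twelfth.

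| Window | p | Part of overall bias due to KC, b = 2 / 3 / 5 | Half-width of limits, b = 2 / 3 / 5 (3.92 if b = 0) | Error in phase contrast |
|---|---|---|---|---|
| 48 h | 0.083 | 0.17 / 0.25 / 0.42 | 4.07 / 4.24 / 4.76 | 2 / 3 / 5 |
| 24 h | 0.167 | 0.33 / 0.50 / 0.83 | 4.18 / 4.49 / 5.36 | 2 / 3 / 5 |
| 8 h | 0.5 | 1.0 / 1.5 / 2.5 | 4.38 / 4.90 / 6.28 | 2 / 3 / 5 |

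The dilution of the mean bias is thus 12-fold, 6-fold or 2-fold, depending on a window that the plan does not state.

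**Effect on a test.** Suppose there is no true change and the bias is δ SDs of the infant-level contrast. A two-sided 5% test of during versus before rejects with probability Φ(δ√n − 1.96) + Φ(−δ√n − 1.96). For assumed n = 20, 30 and 50 infants this is 20%, 28% and 42% at δ = 0.25, and 61%, 78% and 94% at δ = 0.5.

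**KFC versus KMC.** If the error during KC is b_F with the father and b_M with the mother, the within-infant contrast is wrong by b_F − b_M. This is zero when the error is common to both sessions.

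**The case against.** The best reply is that silence is not a plan to pool. Section 5.1 gives no window and says its models will respect the structure of the data, so a phase breakdown is not ruled out. A reader might infer that the plan commits to averaging over the whole record; it does not. What stands is that no phase term or stratum is stated.

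A reader might also infer that the validation could not detect a KC error. That is too strong. Twelve-fold is the extreme case, at maximum wear time. With b = 5 and s = 2, the limits widen from 3.92 to 4.76 even at 48 h, and a large error could show in a Bland-Altman plot. The fair word is diluted.

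Third, the harm is hypothetical. The documents report no KC-specific error, one device records ECG, and the second sits on a limb, where pressure between chests is not an obvious mechanism. The values of b above illustrate averaging; they are not evidence about this sensor.

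Finally, the monitor is not a gold standard. It may share motion artefact, so agreement would not prove both right and disagreement would not show which is wrong. The MediCollector stream is described only as background data, with no signals listed, so complete HR and SpO2 in every room cannot be assumed. All of this stands and limits the remedy, but it does not supply the missing phase estimate.

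**Conclusion.** The point holds as a cheap and worthwhile improvement. An average over the record does not estimate the sensor error that matters for the infant primary contrast. If an error confined to KC existed, the during-versus-before contrast would carry all of it. The overall bias would carry between one-twelfth (48 h, from the documents' own times) and one-half (8 h, assumed). Both the existence and the size of such an error are assumptions.

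Two further inferences should be resisted. The KFC-KMC comparison, whose session order is randomised, is not generally compromised: an error common to both sessions largely cancels, and only a difference between parents remains. Nor does the gap justify making conclusions depend on sensor and monitor agreeing. That would turn an imperfect reference into a co-required endpoint with no rule for discordance.

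**What to change.** In section 5.1:

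1. Add KC phase (before, during, after) and session (KMC, KFC) as fixed effects in the multilevel agreement model. Report bias and limits of agreement for infant HR and SpO2 by phase, letting the residual variance differ by phase so that the limits are phase-specific. Showing the KC-phase bias for each session as well would reveal any parent-specific error.
2. State the window of record that enters the agreement analysis, and define the infant before and after periods. The one-hour periods in section 3.3 are given for the parents' sensor only.
3. Write down the model for the infant HR and SpO2 phase contrast, since 5.1 names phase only for the hormones. Then pre-specify a repeat of that contrast on the BedMaster/MediCollector data, where those signals are available, as a supportive sensitivity analysis. Report both results and discuss any discordance, without requiring both to agree.
4. State that parent HR and HRV cannot be checked this way, because the standard-of-care monitor data cover infants only.

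The cost is a little more analysis on data already captured, with no new measurement. The repeat is a partial check only, for the reasons given about the monitor.
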